4.5.9 Ophthalmologic Examination

All patients will require an ophthalmologic examination at screening and only patients receiving cobimetinib (Arm A) will require subsequent ophthalmologic examinations.

Ophthalmologic examination must be performed at the following timepoints:

- Screening
- Cycle 2 Day 1 \pm 1 week
- Day 1 of Cycles 5, 8, and 11 (every 3 cycles) \pm 2 weeks
- Day 1 of Cycles 15, 19, and 23 (every four treatment cycles) \pm 2 weeks
- Day 1 of Cycles 29, 35, 41, 47, etc. (every six treatment cycles) \pm 2 weeks
- Treatment discontinuation visit. If an ophthalmologic evaluation has been performed within the last 12 weeks of the treatment discontinuation visit, the ophthalmologic examination does not need to be performed during the treatment discontinuation visit.

The objective of baseline ophthalmologic examination is to evaluate for evidence of retinal pathology that may be a risk factor for central serous retinopathy or retinal vein occlusion. Ophthalmologic examination must be performed by a qualified ophthalmologist. Risk factors for retinal vein occlusion include uncontrolled serum cholesterol, hypertriglyceridemia, hyperglycemia, hypertension, and glaucoma. Patients with such conditions will be excluded from the study as detailed in the inclusion/exclusion criteria.

Baseline and serial surveillance ophthalmologic examination will include visual acuity testing, intraocular pressure measurements by tonometry, slit-lamp ophthalmoscopy, indirect ophthalmoscopy, spectral-domain optical coherence tomography, and Humphrey Automatic Visual Field using Swedish interactive threshold algorithm Fast-10-2 protocol.

4.5.10 Patient-Reported Outcomes

PRO data will be collected via the EORTC QLQ-C30 and two additional items from the EORTC item bank (see Section 4.5.10.1) to more fully characterize the clinical profile of cobimetinib plus atezolizumab as compared to regorafenib. In addition, to derive utility for pharmacoeconomic models, patients will complete the EQ-5D-5L.

The questionnaires will be translated as required in the local language. To ensure instrument validity and that data standards meet health authority requirements, questionnaires scheduled for administration during a clinic visit will be completed in their entirety by the patient prior to the performance of non-PRO assessments and the administration of study treatment (where applicable).

Patients will use an electronic PRO (ePRO) device to capture PRO data at in-person clinic visits. The ePRO device and/or instructions for completing the PRO questionnaires electronically will be provided by the investigator staff. The data will be transmitted via a pre-specified transmission method (e.g., web or wireless) automatically after entry to a centralized database at the ePRO vendor. The data can be accessed by the appropriate sponsor study personnel securely via the Internet.

The questionnaires will be completed on the ePRO tablet at the beginning of each cycle upon arrival at the study clinic during treatment period and at the treatment discontinuation visit. The assessments should continue until loss of clinical benefit and then follow the survival follow-up frequency at 3 and 6 months. If the survival follow-up study visits are conducted by telephone, the PRO data (the reduced EORTC QLC 30) for that visit will be collected via telephone interview and recorded by the investigative staff on the ePRO tablet.

Adverse event reports will not be derived from PRO data by the Sponsor.

4.5.10.1 European Organization for Research and Treatment of Cancer Quality of Life-C30 Questionnaire and Additional Items

The EORTC QLQ-C30 is a self-report questionnaire that assesses multiple dimensions of HRQoL among cancer patients. Responses to this 30-item questionnaire are categorized into five functional domains (i.e., physical, role, emotional, cognitive, and social) (scored on a 4-point Likert scale), one global health status domain (scored on a 7-point Likert scale), three symptom domains (i.e., fatigue, nausea/vomiting, pain), and six single items (scored on a 4-point Likert scale). Items that assess abdominal bloating and abdominal pain that are issued from the validated EORTC item bank will be added to the assessment. Each score is transformed into a 0–100-point scale. In the five functional scales and the global health status scale, a high score means a “high level of functioning or global health status.” In the case of symptom scales and single items, a higher score implies a “high level of symptoms or problems.”

To maintain validity and minimize patient burden, the EORTC instrument administered via telephone interview will consist of a reduced version of the EORTC QLQ items (Items 1–7, 10, 12, 13, 16, 17, 18, 29, and 30 from the C30 and the two additional items from the item bank).

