3. STUDY DESIGN

3.1 DESCRIPTION OF THE STUDY

This is a Phase III, multicenter, open-label, three-arm, randomized study in patients with unresectable locally advanced or metastatic CRC who have received at least two prior regimens of cytotoxic chemotherapy for metastatic disease. The study compares regorafenib, a standard of care therapy in this setting, to cobimetinib plus atezolizumab and atezolizumab monotherapy.

The primary objective of the study is to evaluate the efficacy of cobimetinib plus atezolizumab compared to regorafenib in patients with unresectable locally advanced or metastatic CRC who have received at least two prior regimens of chemotherapy in the

metastatic setting. The efficacy of atezolizumab monotherapy compared to regorafenib in the same patient population will also be evaluated as a primary objective.

This study will be conducted globally and approximately 360 patients will be randomized in a 2:1:1 ratio to receive ([Figure 1](#) and [Figure 2](#)):

- Arm A: cobimetinib 60 mg orally on Days 1–21 plus atezolizumab 840 mg IV on Day 1 and Day 15 in a 28-day cycle (n ≈ 180), or
- Arm B: atezolizumab monotherapy 1200 mg IV on Day 1 in a 21-day cycle (n ≈ 90), or
- Arm C: regorafenib 160 mg orally on Days 1–21 in a 28-day cycle (n ≈ 90).

At least 50% patients with extended RAS-mutant tumors (see Section [4.5.7.1](#) for definition) will be enrolled in each arm. Enrollment of patients with MSI-high status (see Section [4.5.7.1](#) for definition) will be limited to approximately 5% to reflect the natural prevalence in mCRC ([Goldstein et al. 2014](#)).

Stratification factors are extended RAS mutation status of the tumor and time since diagnosis of first metastasis (< 18 months vs. ≥ 18 months). Permuted-block randomization will be applied to ensure a balanced assignment to each treatment arm. Randomization and stratification will be managed through an interactive voice/web response system (IxRS).

The Sponsor will monitor the enrollment for each region (North America, Europe, and Pacific/Asia). To ensure balanced global enrollment, the Sponsor may institute temporary limitations on enrollment in certain regions in the event of disproportionate accrual of patients.

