Appendix 1 Schedule of Assessments (cont.)

- ^s PRO instruments EORTC QLQ-C30 and EQ-5D-5L will be completed in this order using an electronic device on Day 1 of each cycle during a visit and prior to any assessments. Data will be collected at end of study and at survival follow-up at 3 and 6 months only. In the event a study visit is conducted by telephone, the PRO data for that visit will be collected via telephone interview and recorded by the investigative staff on the ePRO tablet. To maintain validity and minimize patient burden, the PRO instruments administered via telephone interview will consist of a reduced version of the EORTC QLQ items (Items 1–7, 10, 12, 13, 16, 17, 18, 29, and 30 from the C30 and the two additional items from the item bank) and the telephone interview version of the EQ-5D-5L.
- ^t The initial dose will be delivered over 60 (\pm 10) minutes. If the first infusion is well tolerated all subsequent infusions will be delivered over 30 (\pm 10) minutes until loss of clinical benefit. Dose can be given \pm 7 days from scheduled Day 1 of each cycle.
- ^u Cobimetinib 60 mg/day PO will be given in a 21/7 dosing schedule. Dose can be given \pm 7 days from scheduled Day 1 of each cycle, but the scheduled 7–day break must be \geq 5 days.

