Appendix 1 Schedule of Assessments (cont.)

Arm B: Atezolizumab Monotherapy Schedule of Assessments (21-Day Cycle)

	Screening ^a	Cycle 1		Cycle 2	Cycle 3 +	Treatment Disc ^b	ATA Visit	Survival FU ^c
Day	-35 to 1	1	15	1	1	< 30 d after last dose	120 d after last dose	q3m
Informed consent ^d	x							
Demographics	x							
Medical and CRC history	x							
Vital signs ^{e,f}	x	x		x	x			
ECOG PS	x	x		x	x			
Weight	x	x		x	x			
Height	x							
Complete physical examination	x							
Limited physical examination ^g		x		x	x			
Hematology ^h	x	x		x	x			
Coagulation (INR and aPTT)	x							
Serum sample for autoantibody tests		x				x		
Chemistry ^j	x	x		x	x			
CEA		x		x	x	x		
WGS (optional)		x						
PK and ATA sample	See Appendix 2						x	
ECHO/MUGA	x							
Tumor assessments ⁱ	x	Scan assessments every 8 weeks						
Serology ^k	x							

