Appendix 7 EuroQoL 5 Dimensions Health Questionnaire (cont.)

- We would like to know how good or bad your health is TODAY.
- This scale is numbered from 0 to 100.
- 100 means the best health you can imagine.
0 means the worst health you can imagine.
- Mark an X on the scale to indicate how your health is TODAY.

YOUR HEALTH TODAY =

- Now, please write the number you marked on the scale in the box above.

Appendix 8

European Organisation for Research and Treatment of Cancer 30-Item Quality of Life Questionnaire (Version 3)

EORTC QLQ-C30 (version 3)

We are interested in some things about you and your health. Please answer all of the questions yourself by circling the number that best applies to you. There are no "right" or "wrong" answers. The information that you provide will remain strictly confidential.

	Not at All	A Little	Quite a Bit	Very Much
1. Do you have any trouble doing strenuous activities, like carrying a heavy shopping bag or a suitcase?	1	2	3	4
2. Do you have any trouble taking a long walk?	1	2	3	4
3. Do you have any trouble taking a short walk outside of the house?	1	2	3	4
4. Do you need to stay in bed or a chair during the day?	1	2	3	4
5. Do you need help with eating, dressing, washing yourself or using the toilet?	1	2	3	4

During the past week:

	Not at All	A Little	Quite a Bit	Very Much
6. Were you limited in doing either your work or other daily activities?	1	2	3	4
7. Were you limited in pursuing your hobbies or other leisure time activities?	1	2	3	4
8. Were you short of breath?	1	2	3	4
9. Have you had pain?	1	2	3	4
10. Did you need to rest?	1	2	3	4
11. Have you had trouble sleeping?	1	2	3	4
12. Have you felt weak?	1	2	3	4
13. Have you lacked appetite?	1	2	3	4
14. Have you felt nauseated?	1	2	3	4
15. Have you vomited?	1	2	3	4
16. Have you been constipated?	1	2	3	4

Appendix 8 European Organisation for Research and Treatment of Cancer 30-Item Quality of Life Questionnaire (Version 3) (cont.)

Please go on to the next page

During the past week:	Not at All	A Little	Quite a Bit	Very Much
17. Have you had diarrhea?	1	2	3	4
18. Were you tired?	1	2	3	4
19. Did pain interfere with your daily activities?	1	2	3	4
20. Have you had difficulty in concentrating on things, like reading a newspaper or watching television?	1	2	3	4
21. Did you feel tense?	1	2	3	4
22. Did you worry?	1	2	3	4
23. Did you feel irritable?	1	2	3	4
24. Did you feel depressed?	1	2	3	4
25. Have you had difficulty remembering things?	1	2	3	4

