4.4.2.4 Patient-Reported Outcomes

Data from the EORTC QLQ-C30 questionnaire and two additional items from the EORTC Item Bank will be scored according to the EORTC scoring manual (Fayers et al. 2001).

The primary analysis population for evaluation of patient-reported outcome (PRO) assessments will include patients in a modified ITT population with a baseline PRO assessment and at least one post-baseline PRO assessment.

Data from the physical function scale and the global health status/quality of life sub-scale of the EORTC QLQ-C30 will be analyzed as time to clinically meaningful deterioration, which will be compared as secondary efficacy endpoints among treatment groups with use of the log rank test (2-sided). Confirmed clinically meaningful deterioration will be defined as a ≥ 10 -point decrease (on a transformed 0 to 100 score) from baseline on the physical function score or the global status/quality of life scores that must be held for at least two consecutive assessments or an initial ≥ 10 -point decrease from baseline followed by death within 4 weeks of the last assessment. Data for patients who do not achieve a 10-point decrease will be censored at the last time PRO data are available. The HR will be estimated using a stratified Cox proportional hazards model and its 95% CI will be provided.

Summary statistics (mean, standard deviation, median, and range) of absolute scores and mean changes from baseline will be calculated for all items and subscales of the EORTC QLQ-C30 and the two additional items from the EORTC Item Bank at each assessment timepoint for each arm while patients are receiving treatment. The mean (and 95% CI) and median of the absolute scores and the changes from baseline to each follow-up point will be reported for categorical and continuous variables, and the proportion of patients selecting each response option will be reported for the two additional items from the EORTC Item Bank. Previously published minimally important

differences (of 10 points) will be used to identify meaningful change from baseline within each treatment group on the functional and disease or treatment-related symptoms scales (Osoba et al. 1998; Cocks et al. 2011). Additional sensitivity analyses may be conducted.

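### On-treatment questionnaires follow cycles of 21 days in Arm B and 28 days in Arms A and C, which tilts time to deterioration modestly against Arm B and under-samples oral-drug symptoms in Arms A and C

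*Protocol*

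**What the plan says.** Protocol 4.5.10 states: "The questionnaires will be completed on the ePRO tablet at the beginning of each cycle upon arrival at the study clinic". A further set is taken when the patient stops treatment. On how long collection goes on, the section says: "The assessments should continue until loss of clinical benefit and then follow the survival follow-up frequency at 3 and 6 months". The Appendix 1 footnotes for all three arms fix the day for both instruments, which "will be completed in this order using an electronic device on Day 1 of each cycle during a visit and prior to any assessments".

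Cycle length differs by arm. Protocol 3.1 gives "Arm B: atezolizumab monotherapy 1200 mg IV on Day 1 in a 21-day cycle". Arms A and C run 28-day cycles with cobimetinib or regorafenib on Days 1 to 21; Arm A also receives atezolizumab on Days 1 and 15. Appendix 1 lets the 7-day oral break shorten to 5 days.

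SAP 4.4.2.4 analyses physical functioning and global health status as time to deterioration. An event is a drop of at least 10 points from baseline "that must be held for at least two consecutive assessments", or an initial drop followed by death within 4 weeks. Arms are compared by a two-sided log-rank test as secondary efficacy endpoints. Protocol 6.5 instead counts a single 10-point drop, death or progression, but SAP Sections 1 and 4 say that the SAP prevails for filing.

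Neither document specifies common assessment windows, an interval-censored method or a named sensitivity analysis for unequal spacing. The SAP leaves further sensitivity analyses and a longitudinal model optional.

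**The concern.** An event found only at scheduled visits is found sooner when visits are closer together. Requiring two consecutive low scores compounds this, because confirmation takes 3 weeks in Arm B and 4 weeks in Arms A and C. A log-rank test then reads part of the schedule as a treatment effect. That bears on B vs C and, through SAP 4.4.4, on A vs B, where secondary endpoints help to judge what each drug contributes; there the mismatch would tend to favour the combination.

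The second issue is where in the cycle the questionnaire falls. Protocol 2.6 aims to describe treatment impact on diarrhea, constipation, appetite, fatigue, bloating and abdominal pain for the combination against regorafenib. In both of those arms the Day 1 questionnaire comes at the end of the oral-drug pause.

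**Working it through.** The documents give no power or bias figure for time to deterioration, so there is none to reproduce.

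**1. Schedule.** Post-baseline assessments by week 12 (84 days): 84/21 = 4 in Arm B, 84/28 = 3 in Arms A and C. The earliest confirmed deterioration needs low scores at weeks 3 and 6 in Arm B, and at weeks 4 and 8 in Arms A and C.

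**2. Detection delay.** For an exponential time to deterioration with rate λ and visits every w days, the mean delay to the first visit after onset is w/(1 − exp(−λw)) − 1/λ. Assume a median of 3 months: λ = 0.6931/(3 × 30.44) = 0.00759 per day, so 1/λ = 131.7.
- w = 21: 21/0.1473 − 131.7 ≈ 10.8 days
- w = 28: 28/0.1915 − 131.7 ≈ 14.5 days

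The gap is about 3.7 days. It is 3.9 days with a 1.5-month median and 3.6 days with a 6-month median. A nearly constant gap matters more when deterioration is fast.

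**3. Simulation with no true difference, SAP rule.** From the documents: 90 patients per arm, 21- or 28-day visits with ±3 days, two consecutive drops or one drop followed by death within 4 weeks. Assumed: exponential onset, the medians shown, and 30% of single unconfirmed drops followed by death within 4 weeks. The SAP does not say which of the two low scores dates the event; the first is used. There were 1,500 runs per row.

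| Median time to deterioration | Median length of PRO collection | HR B/C | Two-sided error | Error against B (nominal 2.5%) |
|---|---|---|---|---|
| 1.5 mo | 2 mo | 1.19 | 12.1% | 11.8% |
| 3 mo | 2 mo | 1.13 | 7.1% | 5.9% |
| 3 mo | 4 mo | 1.08 | 6.1% | 4.7% |
| 6 mo | 4 mo | 1.05 | 5.3% | 3.9% |
| Control, 28 days in both arms, 3 mo | 2 mo | 1.00 | 4.9% | 2.5% |

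The Monte Carlo standard error at 2.5% is √(0.025 × 0.975/1500) = 0.4 percentage points.

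A second model lets the score drift by 2 to 4 points per 28 days with a within-patient SD of 6 to 10 points and PRO collection ending at a median of 4 months. It gives 1.13 to 1.23, with two-sided error of 5.6% to 10.9%, and 0.99 to 1.01 when both arms use 28 days.

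**4. Protocol 6.5 definition.** With an assumed median progression time of 2 months read on 8-week scans, and PRO collection at a median of 2 months, the HR is 1.07, 1.03 and 1.02 for median deterioration times of 1.5, 3 and 6 months. Progression and death dilute the artefact.

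**5. A vs C.** Both arms are on 28 days, so spacing creates no bias.

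**6. Recall.** In Protocol Appendix 8, items 6 to 28 and the two added items stand under "During the past week", and items 29 and 30 name the same period. On Day 1 of the next cycle that window is Days 22 to 28. Oral-drug days inside it: 7 − 7 = 0 with the full break, 7 − 5 = 2 with the shortest permitted break. No routine on-treatment questionnaire falls within Days 2 to 21.

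**The case against.** The best defence is that these endpoints sit outside the testing hierarchy, which now holds only the two OS comparisons, so no controlled alpha is spent on them. Per-visit summaries of change from baseline are planned as well, and a longitudinal model is allowed for. The stated symptom objective concerns A vs C, where spacing is equal. All of this stands, and it limits the consequence. It does not remove the tilt in a comparison the SAP plans to make by log-rank, and the analyses that might reveal the tilt are optional.

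The magnitude also rests on assumed deterioration and collection times. That stands too: the direction was the same in every scenario, but the size was not. The simulations omit the discontinuation and follow-up questionnaires, which would alter the size by an amount not computed here.

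On recall, nothing in the documents shows that diarrhea or fatigue clears within the off-week, so some on-drug burden may still be reported on Day 1. In addition, physical functioning (items 1 to 5) stands above the past-week heading, so the recall argument does not apply to that scale as it does to the symptom items.

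**Conclusion.** The point holds as a modest, one-directional schedule artefact plus a sampling gap. With no true difference, the B/C hazard ratio for time to deterioration is about 1.05 to 1.23 under the SAP rule, conditional on the assumptions above. The same mismatch would enter any A vs B comparison. OS conclusions are unaffected.

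A reader might infer more than the documents support:
- That questionnaires are given only on Day 1. This is true on treatment, but they are also given at discontinuation and at 3 and 6 months of follow-up.
- That Arms A and C are both drug-free before Day 1. Arm A pauses cobimetinib only; atezolizumab was given on Day 15.
- That on-drug burden is never measured, or that the symptom objective cannot be met. A discontinuation visit, allowed at any time within 30 days of the last dose, or a shortened break can bring on-drug days into recall. The burden is under-sampled and the objective weakened.

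**What to change.** **(a) SAP 4.4.2.4.** Add a supportive time-to-deterioration analysis for B vs C and for A vs B, restricted to the shared grid of weeks 12, 24 and so on (4 × 21 = 3 × 28 = 84 days), reported beside the main analysis. Define the grid by calendar windows, since dose delays move cycle Day 1. On an 84-day grid the simulated B/C hazard ratio returns to about 1.0. The cost is precision: confirmation needs weeks 12 and 24, and with PRO collection ending at a median of 4 months only 0.5^(5.52/4) = 38% of patients remain at week 24 (168/30.44 = 5.52 months). Simulated events fell from 70–96 to 38–58, roughly 40% to 50% fewer. It should not replace the main analysis.

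**(b) Protocol 4.5.10 and Appendix 1.** Add the QLQ-C30 and the two extra items at Cycle 1 Day 15, a visit already in all three schedules, where recall falls on oral-drug days in Arms A and C. Use it for between-arm symptom summaries only, and state that Day 15 data are excluded from time to deterioration. The cost is a few minutes of patient time. If all patients have already passed this visit, report the under-sampling as a limitation instead.

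Do not add later Day 15 questionnaires in Arm A alone. Its Day 15 visits recur every cycle, while Arm C has them only in Cycles 1 and 2. If such data entered time to deterioration, the now balanced A vs C comparison would be biased: simulated null A/C hazard ratios were 1.10 to 1.28, depending on assumptions.

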4.5.10.2 EuroQoL 5 Dimensions

The EQ-5D questionnaire is a generic, preference-based health utility measure with questions about mobility, self-care, usual activities, pain/discomfort, and anxiety/depression that are used to build a composite of the patient’s health status. The EQ-5D will be utilized in this study for economic modeling. The EQ-5D questionnaire takes 5 minutes or less to complete.

To maintain validity and minimize patient burden, the EQ-5D-5L instrument administered via telephone interview will consist of the telephone interview version of the EQ-5D-5L.

4.5.11 Timing of Assessments

4.5.11.1 Screening

Screening tests and evaluations will be performed within 35 days prior to Cycle 1 Day 1. Results of standard-of-care tests or examinations performed prior to obtaining informed consent and within 35 days prior to Cycle 1 Day 1 may be used; such tests do not need to be repeated for screening.

See [Appendix 1](#) for the schedule of screening assessments and [Appendix 2](#) for the schedule of PK and ATA assessments.

